9.7.3 Exploratory Efficacy Outcome Measures

The exploratory efficacy outcome measures for this study are the following:

- cCR rate
- Relapse Free Survival (RFS)
- Progression Free Survival (PFS)
- Duration of Responses (CR, cCR)
- Time to CR
- CR within 6 cycles

9.7.3.1 Composite Complete Remission rate

Composite complete remission (cCR) rate is defined as the proportion of patients who achieve either a disease response of CR, CRi or MLFS (ie, $cCR = CR + CRi + MLFS$) within the study period ([Appendix F](#)). Absence of interceding therapies, including salvage treatments and HSCT is requested for considering the response in the analysis.

Composite CR rate will be analyzed on the ITT and the EE-1 sets. Composite CR rate will be analyzed using the same methods as those used for the CR rate analysis. Patients for whom no efficacy assessment is available will be analyzed as not having cCR when considering the ITT set.

9.7.3.2 Relapse-free Survival (RFS)

RFS is defined as the time from the date of achievement of CR or CRi until the date of relapse (progression), or death from any cause, whichever occurs first.

Censoring rules will include the following:

- Time to relapse (progression) will be censored at the date of the last assessment of patient status excluding relapse (progression). In case of no post-baseline disease assessments after CR, censoring will be at the date of CR/CRi.

RFS will be analyzed using the same methods as those used for OS (Kaplan Meier estimates and stratified log-rank test). In addition, possible RFS analyses based on other RFS censoring criteria (e.g. censoring at the date of start of a new therapy) will be specified in the SAP. The analysis set will be the ITT set limited to patients who achieve a CR/CRi in absence of interceding therapies, including salvage treatments and HSCT.

9.7.3.3 Progression-free Survival (PFS)

PFS is defined as the time from the date of randomization until the date of relapse (progression), or death from any cause, whichever occurs first.

Censoring rules will include the following:

- Time to relapse (progression) will be censored at the date of the last assessment of patient status excluding relapse (progression). In case of no disease assessments, censoring will be at the date of randomization.

PFS will be analyzed using the same methods as those used for OS (Kaplan Meier estimates and stratified log-rank test). In addition, possible PFS analyses based on other

PFS censoring criteria (e.g. censoring at the date of start of a new therapy) will be specified in the SAP. The analysis set will be the ITT set.

9.7.3.4 *Duration of Morphologic complete Remission (CR)*

Duration of CR is defined as the time from the date of achievement of CR until the date of relapse (progression). Kaplan-Meier methods will be used to estimate duration of response in each treatment group. Estimates of median duration will be provided with 95% confidence intervals, along with the 25th and 75th percentiles. Stratified log-rank test will be used to compare treatment groups.

Censoring rules will include the following:

- Time will be censored at the date of the last adequate assessment of patient status excluding relapse (progression). In case of no disease assessments after CR, censoring will be at the date of CR.

In addition, possible analyses based on other censoring criteria (e.g. censoring at the date of start of a new therapy) will be specified in the SAP. The analysis set will be the ITT set limited to patients who achieve a CR in absence of interceding therapies, including salvage treatments and HSCT.

9.7.3.5 *Duration of Composite Complete Remission*

Duration of cCR response is defined as the time from the date of achievement of either CR, CRi or MLFS until the date of relapse (progression), and will be analyzed as the duration of CR response.

Censoring rules will include the following:

- Time will be censored at the date of the last assessment of patient status excluding relapse. In case of no disease assessments after cCR, censoring will be at the date of cCR.

In addition, possible analyses based on other censoring criteria (e.g. censoring at the date of start of a new therapy) will be specified in the SAP. The analysis set will be the ITT set limiting to patients who achieve a cCR in absence of interceding therapies, including salvage treatments and HSCT.

9.7.3.6 *Time to CR*

Time to CR is defined as the time from the date of randomization until the date of CR in the absence of interceding therapies, including salvage treatments and HSCT. The analysis set will be the ITT set.

Time to CR will be censored at the date of the last assessment of patient status excluding CR in the case no CR occurred by time of analysis. In case of interceding therapies, PD or death, time to CR will be censored to the new AML treatment start date, PD assessment date or death date, respectively. Cumulative Incidence Function (CIF) will be computed as 1-Kaplan Meier curve and treatment groups will be compared by the log-rank test.

9.7.3.7 Morphologic Complete Remission (CR) within 6 cycles rate

Morphologic complete remission (CR) within 6 cycles rate is defined as the proportion of patients who achieve CR in the absence of interceding therapies, including salvage treatments and HSCT, within 6 treatment cycles. Analysis will be performed in the ITT set.

CR within 6 cycles rate will be analyzed using the same methods as those used for the CR rate analysis, limiting to the stratified analysis. Patients for whom no efficacy assessment is available will be analyzed as not having CR.

9.7.4 Subgroup Analyses

The primary endpoint of OS and the secondary endpoints of CR, CR_c, CR_{MRD} and transfusion independence will be also explored in subgroups based on stratification variables, as well as demographic and baseline patient characteristics. Details will be provided in the SAP.

In each defined subgroup, the analysis will be carried out using the same type of methodology as described for the overall analysis of the corresponding endpoint. These results will be considered exploratory because of the multiplicity issue and also smaller sample sizes that cannot be pre-specified. For subgroups without an adequate number of patients, the analyses will not be performed.

9.7.5 Quality of Life

Quality of life will be evaluated using the EORTC QLQ-C30 questionnaire.

Summary tables of absolute value and change from baseline at the different timepoints will be produced. Baseline will be the last value available before the first study drug administration on Day 1 of Cycle 1. The global health status and some of the functional scales or symptom scales, which will be defined in the SAP, will be analyzed.

9.7.6 Compliance to study treatment

Compliance with therapy (as defined in Section 4.8) will be summarized (number of patients compliant and percentage related to patients in the cycle) by cycle and by treatment group for pracinostat / placebo and for AZA.

Compliance over the whole study period will also be summarized. Specific rules to evaluate the overall compliance will be presented in the SAP.

9.8 Safety Analyses

Tolerability, safety and adverse events (AEs) will be assessed as follows:

- Incidence, nature, seriousness and severity of AEs and relationship to study treatment
- Discontinuations from drug or dose modifications due to AEs
- Values/findings and changes in vital signs, physical examinations (only listing of findings), electrocardiograms (ECGs) and laboratory values

9.8.1 Analysis of Adverse Events

The analyses of safety will be performed on the Safety set.

Terminology from the Medical Dictionary for Drug Regulatory Activities (MedDRA) will be used to assign System Organ Class (SOC) and Preferred Terms (PT) classification to AEs and diseases, based on the original terms entered on the CRFs.

The number and percentage of patients reporting TEAEs and study drug related TEAEs will be summarized by SOC and PT. Tables by worst CTCAE grade will be also produced. The number and percentage of patients reporting treatment-emergent SAEs and drug-related SAEs will be tabulated, as well as TEAEs leading to dose modification, to discontinuation of study treatment or leading to death. Pre-treatment AEs and post-treatment AEs (if any) will be listed. TEAEs of special interest will be presented also in specific summary table(s) and listing(s).

A by-patient AE (including treatment-emergent, pre-treatment and post-treatment (if any)) data listing including, but not limited to, verbatim term, PT, SOC, CTCAE grade, and relationship to study treatment will be provided. Deaths, other SAEs, including those leading to discontinuation of study treatment, will be listed.

The above described analyses will be performed overall. Further details and analysis by cycle will be described in the SAP.

In consideration of the study population, to better evaluate tolerability in elderly unfit subjects, part of the overall analysis described above will be performed also by age group, by ECOG class and by renal impairment category at baseline (based on glomerular filtration rate).

9.8.2 Clinical Laboratory Evaluation Analyses

Descriptive statistics will be provided for the clinical laboratory results by scheduled time of evaluation for the Safety set, as well as for the change from baseline. The baseline value is defined as the last non-missing value before the initial administration of study treatment. In addition, mean change from baseline will be summarized for the maximum and minimum post-treatment values and the values at the End of Treatment visit (or the last value obtained under treatment).

Abnormal clinical laboratory results will be graded according to NCI CTCAE version 4.03, if applicable, and the grade will be presented in a by-patient data listing. A shift table, presenting the 2-way frequency tabulation for baseline and the worst post-treatment value according to the NCI CTCAE grade, will be provided for clinical laboratory tests. Abnormal clinical laboratory test results of Grade 3 or 4 will be listed.

9.8.3 Vital Sign Analyses

Descriptive statistics will be provided for the vital signs measurements by scheduled time of evaluation for the Safety set, as well as for the change from baseline. The baseline value is defined as the last non-missing value before the initial administration of study treatment. In addition, mean change from baseline will be presented for the maximum and minimum post-treatment values and the values at the End of Treatment visit.

9.8.4 Electrocardiogram Analyses

Descriptive statistics will be provided for the central ECG measurements by scheduled time of evaluation for the Safety set, as well as for the change from baseline. The baseline value is defined as the last non-missing value before the initial administration of study treatment. For triplicate measurements the mean value will be used for analysis. ECG abnormalities will be graded according to the CTCAE criteria. The number and percentage of patients with QTcF interval values less than or equal to 450, between 451 and 480, between 481 and 500, as well as >500 ms will be tabulated and changes from baseline of less than 30 ms, 30-60 ms and >60 ms over all post treatment evaluations and by cycle will be summarized and described in relation to baseline values. ECG data will also be presented in the data listings.

9.9 Pharmacokinetic Analyses

The sparse concentration-time data collected for pracinostat and its metabolites will be analyzed by non-linear mixed effect modeling according to a population PK data analysis approach. The purpose of this analysis is to obtain exposure data in patients with AML, to characterize the PK parameters of pracinostat and its metabolites, and to identify relevant covariates affecting pracinostat exposure. In addition, exposure variables will be correlated to both efficacy and safety (AE) variables in a PK/PD analysis. The possible drug interaction of Pracinostat on the PK of AZA will be evaluated by comparing the descriptive statistics of PK parameters of azacitidine in the two groups. The analysis will be performed in the PK analysis set(s).

Additional details on the PK/PD methods and analysis will be provided in a dedicated SAP.

9.10 Health Economics Analysis

The analytical approach will be a cost efficacy analysis. The health economics analysis will be managed and conducted separately. Relevant patient data and analyses results will be presented in a separate report. Further details will be outlined in the Health Economics analysis plan.

9.11 Power and Sample Size Determination

This is an event-driven study. Sample size was computed for a group-sequential design with stopping rules for both futility and superiority (study-wise one-sided alpha level=0.025, power 0.90) with one interim analysis at 67% (2/3) of information and a final analysis. The error spending function is from the Gamma Family, using $\gamma=-3.6$ (similar to O'Brien Fleming) for superiority and $\gamma=-5.5$ (more conservative than O'Brien Fleming) for futility (non-binding). Proportionality of hazards is assumed. Assuming that median OS is 10.0 months in the Group B (placebo + AZA) the aim is to detect, by means of the log-rank test or equivalent, an increase to 14.0 months in Group A (pracinostat + AZA), i.e., a HR of 0.714. A total of 390 events (deaths) allows to meet a power requirement of at least 90% (actually 90.78%) at a study-wise one-sided significance level of 0.025.

Patient accrual is assumed to occur over a 30-month period. Assuming a non-constant accrual rate (100 patients during the first year and the remain patients during the following 1.5 years) and a 3% yearly drop-out rate, and considering that 500 patients will be recruited, it is expected that the post-recruitment follow-up period will take about 18 additional months to reach 390 events for final OS analysis.

Sample size calculations were made using SAS 9.2.

The overall event rate (blinded) will be constantly monitored. Before the expected recruitment end, the observed placebo hazard rate will be derived from the (blinded) overall observed hazard rate at that time, assuming a hazard ratio of 0.714. Based on the computed value the decision to adapt the sample size to enable study end within a reasonable amount of time from the end of recruitment might be taken. This procedure does not introduce bias and no statistical adjustments to preserve the study-wise alpha error are required.

A group-sequential procedure will be applied also to the secondary endpoints, adopting as the error spending function for superiority the Gamma Family, using $\gamma=3.6$. Details on the procedure and power calculation for the secondary endpoints will be provided in the SAP.

9.12 Interim Analysis

One formal interim analysis on the primary endpoint, OS, is planned and will be assessed by the IDMC. The interim analysis is to be performed when 2/3 of the total number of events (260/390 deaths due to any cause) have occurred in the study, according to the group sequential testing design described in Section 9.11. Events should be reported to sponsor as soon as they become known to investigators and entered in the eCRF in a short time. As soon as the 260th event is reported to the sponsor, the set of 260 events will be considered as complete. This set of events will be submitted to final validation before analysis. Data emerged on a later time point (including events occurred earlier than the 260th event) will not be considered for the interim analysis. The same rule will be applied at the time of final analysis, if relevant. Further data will be considered in an addendum to the CSR.

Further details will be provided in the SAP and DMC Charter prior to the implementation of this interim analysis.

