5.2 In-Study Long-term Follow-Up

After patients permanently discontinue pracinostat/azacitidine or placebo/azacitidine, they will be followed every 3 months (± 1 month) from the date when study drug was last administered until the end of the study. The following information will be obtained during these Follow-up contacts:

- Collect any new AML treatment
- Collect any evidence of disease progression
- Assess survival status

- When there is a suspicion of disease progression, a bone marrow evaluation is required to confirm disease progression

Every effort must be made to follow patients from the time of treatment discontinuation until death. Patients may be contacted during outpatient visits or by telephone.

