9.7 Efficacy Analyses

9.7.1 Primary Efficacy Analysis - Overall Survival

The primary efficacy endpoint is overall survival (OS) measured as the time from randomization until death from any cause.

OS time for patients alive or lost to follow-up at the time of analysis will be censored at the date when they were last known to be alive.

OS will not be censored at the time of subsequent AML therapy. Both interim and final OS analyses will be performed on the ITT set. Final analysis will take place after the required number of events (390 deaths) has occurred.

The primary OS analysis will be based on the log-rank test stratified by the factors used for randomization (cytogenetic risk and ECOG) at the overall one-sided $\alpha = 0.025$ level of significance (specific α levels will be used for interim and final analysis). Log-rank stratified by cytogenetic risk obtained by central laboratory (when available) and ECOG at Day 1 Cycle 1, unstratified log-rank test and Cox PH model including factors used for randomization will be used as sensitivity analyses to support evidence of efficacy. Kaplan-Meier estimates of OS in each treatment group will be reported, both overall and within strata of patients. Estimates of median survival will be provided with two-sided 95% confidence intervals, along with the 25th and 75th percentiles, together with the HR estimates. The number of surviving patients, the number of deaths and the number of patients with censored values will be displayed as well.

Checks on the proportionality of hazards will be performed.

Censoring patterns will be examined between treatment groups. The effect of subsequent therapy on OS will be analyzed, including an analysis that compares OS in the treatment groups with censoring at the start date of the new regimen subsequent AML therapy. Other sensitivity analyses will be performed to assess the robustness of OS results, if relevant.

The primary OS analysis (stratified log-rank test) will be repeated for the PP set.

Further exploration of baseline/demographic factors of interest will be done by means of Cox PH model.

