8.1.1 Interim Analysis

The efficacy analyses done for the interim analysis by the unblinded statistician at the CRO will be provided to the IDMC, which will provide a recommendation to Sponsor whether the study should proceed or stop due to efficacy or futility (non-binding). The efficacy criterion, which will be the basis for the IDMC recommendation together with the overall risk-benefit assessment is that the p-value of the stratified log-rank test is below the computed significance level of the interim analysis (p-value <0.00605). For the futility the significance level of 0.29906 is computed as the bound. In terms of HR, the following values are calculated: 0.73254 for the efficacy and 0.93671 for the futility evaluation, respectively. Significance levels and their counterpart in terms of HR will be re-computed at time of analysis based on the real fraction of information available. Conditional power of getting a significant result at the final analysis taking into account the results of the interim analysis will also be computed. In case of stopping of the study at the interim stage, correction to the estimation (median estimate and related CI) will be applied to reduce potential bias. Adequate SAS code will be used to produce the stratified log-rank test (PROC LIFETEST), save the test results and pass these results to the PROC SEQTEST together with the needed data from the PROC SEQDESIGN. Elaboration of data from PROC LIFETEST could be needed considering that the alternative hypothesis is one-sided.

Boundaries at time of the Interim Analysis (IA) will be recomputed having as fraction of information the number of events at IA in the ITT set / overall number of planned events (390). For calculations, the power of the test will be changed as needed to maintain the initial total number of events (390).

The proportionality of hazards will be exploratively evaluated plotting the log negative log survival distribution function for each of the treatment groups in each stratum against the log of survival days.

Selected secondary endpoints could be analyzed to provide additional information to the IDMC, if requested .

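### The overall survival data are closed by the order in which deaths are reported, with no survival sweep, so interim Kaplan-Meier medians depend on reporting speed and can err in either direction

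*Protocol*

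**What the plan says.** Protocol 9.12 sets the interim for when 260 of 390 deaths have occurred, but closes the data on reporting: "As soon as the 260th event is reported to the sponsor, the set of 260 events will be considered as complete". It then excludes what arrives afterwards: "Data emerged on a later time point (including events occurred earlier than the 260th event) will not be considered for the interim analysis". For the final analysis: "The same rule will be applied at the time of final analysis, if relevant". What is left out is deferred: "Further data will be considered in an addendum to the CSR".

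Protocol 9.7.1 says OS time for patients alive or lost to follow-up "will be censored at the date when they were last known to be alive". SAP 8.1 likewise censors at the last recorded assessment of survival status. After treatment stops, Protocol 5.2 says of patients that "they will be followed every 3 months", with a one-month window either way.

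SAP 8.1.1 says the significance levels and their hazard ratio equivalents "will be re-computed at time of analysis based on the real fraction of information available", taking information as the events in the ITT set at the interim divided by 390. The SAP does not restate the reporting-order freeze. Neither document describes a round of survival-status checks before either lock.

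**The concern.** Two things follow when the freeze is combined with last-known-alive censoring.

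- A patient who died before the freeze, but whose death reached the sponsor after it, is censored at the last contact before death.
- A living patient off treatment is censored at the last contact, which may be three to four months old, while deaths elsewhere are entered as soon as they are known.

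Death and survival are thus ascertained to different dates, and the gap depends on how fast sites report. At stake are the completeness of the primary endpoint data and the interim medians, which would be reported if the trial stopped early. SAP 8.1.1 plans a correction to the median after an early stop, but for the sequential design, not for ascertainment. The freeze also buys nothing in error control, because the boundaries are recomputed from whatever event count is used.

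**Working it through.** **The plan's own figures.** Inputs: 390 deaths, interim at 260, one-sided 0.025, 1:1 allocation, medians 10 and 14 months (Protocol 9.11; SAP 3.3 and 5.5).

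- Fixed-design power: √390/2 × ln(14/10) − 1.960 = 3.322 − 1.960 = 1.362, giving 91.35%.
- O'Brien-Fleming spending at 2/3 information: 2 × [1 − Φ(2.2414/√0.6667)] = 0.00605. The final level is then 0.02314.
- Interim efficacy bound: exp(−2 × 2.509/√260) = 0.7325. SAP 8.1.1 gives 0.73254.
- Two-look power net of the futility stop: 90.87% (SAP 3.3). With the protocol's Gamma(−3.6) and the SAP futility bound as a stand-in for the protocol's, it is 90.78% (Protocol 9.11).

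The frozen sets hold 260 and 390 deaths by construction, so these figures stand.

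**Deaths set aside.** The expected number of deaths that have occurred but are unreported is roughly the death rate times the mean lag. With the protocol's accrual (100 patients in year 1, 400 over the next 18 months) and 3% yearly drop-out, about 13.3 deaths a month are expected near month 32. Lags of 0.5, 1 and 2 months give 6.7, 13.3 and 26.6.

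**Simulation.** 2,000 trials per scenario. Assumptions not in the documents: exponential survival, exponential time on treatment (the 8-month mean is from Protocol 3.1), contacts every 28 days on treatment and every 3 months after it, and the same lag in both arms. The sweep takes in all deaths up to the freeze date and updates alive dates to it.

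| Mean lag (months) | Interim events, frozen → swept | Interim medians frozen (control/exp.) | Swept | Final events, frozen → swept |
|---|---|---|---|---|
| 0 | 260 → about 260 | 9.55 / 13.27 | about 10.0 / 14.1 | 390 → about 390 |
| 0.5 | 260 → 266.7 | 9.74 / 13.59 | 9.98 / 14.10 | 390 → 392.6 |
| 1 | 260 → 273.4 | 10.00 / 13.95 | 10.03 / 14.10 | 390 → 395.4 |
| 2 | 260 → 286.2 | 10.41 / 14.60 | 10.04 / 14.04 | 390 → 400.5 |
| Death found at next contact | 260 → 275.5 | 10.04 / 14.06 | 10.06 / 14.09 | 390 → 397.5 |

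A second simulation of the same rule gave 7–27 interim and 3–13 final deaths set aside, with the same pattern of medians.

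**Two opposing effects.** Holding alive dates at last contact in both cases isolates the effect of leaving out the late deaths. It lengthens the medians: 9.65 → 10.00 and 13.34 → 13.95 at one month; 9.70 → 10.41 and 13.37 → 14.60 at two months. The stale alive dates shorten them, and they act alone at zero lag, when no death is discarded. The two roughly cancel near one month.

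**Inference.** With equal lags, the mean hazard ratio differs by no more than 0.002 between frozen and swept data. Under the null, the frozen data crossed the interim bound in 0.0045–0.006 of trials, against a nominal 0.00605. Final medians move by less than 0.05 month.

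**What a larger count does to the boundary.** The same spending formula gives an interim level of 0.00675 at 267 events, 0.00749 at 274 and 0.00886 at 286. No design change is needed.

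**The case against.** The case for leaving the rule alone is substantial. The design calls for 260 and 390 events and the rule delivers them. The interim recommendation rests on the stratified log-rank p-value and a risk-benefit assessment, not on medians. Protocol 9.12 asks for deaths to be reported promptly, sends later data to an addendum, applies the rule at the final analysis only where relevant, and defers detail to the SAP and a DMC charter that is not available here. SAP 8.1 expects the censoring date finally to match the end-of-follow-up date, which hints at a closing status update. Patients on treatment are seen at least once a cycle, so stale contacts arise mainly after treatment stops.

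Most of this stands, and it rules out three stronger readings.

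- A reader might infer that the trial loses events or power. It does so only against a sweep at the same date; the planned information is intact.
- A reader might infer that discarding deaths shortens the medians. That step lengthens them; the shortening comes from stale alive dates.
- A reader might infer that the hazard ratio or the error rate is biased. With equal lags neither is. An arm-dependent lag could bias the hazard ratio, but it was not simulated and the documents give no reason to expect one.

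What the objection does not answer is that deaths dated before the freeze and in hand before the analysis is run are still left out. An addendum is not the primary analysis, and a hint in SAP 8.1 is not a specified sweep before either lock.

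**Conclusion.** The concern holds as one of ascertainment, and mainly at the interim. The rule sets aside about 7–27 deaths at the interim and 3–13 at the final analysis relative to a sweep at the same date. It leaves interim medians about 0.4–0.5 (control) and 0.8 (experimental) months short if deaths are reported at once, close to correct near a one-month lag, and about 0.4 and 0.5–0.6 months long at two months. Planned events, power, hazard ratio and type I error are essentially kept, and final medians barely move.

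These sizes rest on assumed lags of 0–2 months (0.5–2 for the deaths set aside), equal in both arms, and on exponential survival at the design medians. SAP 8.1.2 reports evident non-proportional hazards for treatment, so the actual median shifts could differ. The mechanism does not depend on that. The change is worth making because it is cheap and the present rule gains nothing in error control.

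**What to change.** In Protocol 9.12 and SAP 8.1, replace the reporting-order freeze with a calendar data cut-off, for example the date on which the 260th (390th) death is reported. Then:

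1. Before lock, ascertain survival status to that date for every patient not known to be dead.
2. Count every death dated on or before the cut-off and reported before lock.
3. Censor the others at the cut-off if known alive then, otherwise at the last date known alive on or before it.
4. Use the actual event count as the information fraction, as SAP 8.1.1 already provides.

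If the cut-off were instead the date of the 260th death in order of death, the count would stay at 260 apart from ties. The sweep would still correct the alive dates, but the extra deaths would not be gained.

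SAP section 11 says version 5 follows the unblinding of the interim results. For the interim, the swept data can therefore serve only as a supplementary analysis; the rule can still be set for a final lock that has not yet taken place.

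The cost is one paragraph in each document, one round of survival-status contacts, and a short delay before each lock.
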